8.2. Handling of Dropouts/Missing Data

For the efficacy endpoint, proportion of treatment failures, subjects who discontinued from the study or died by week 12 will be considered as treatment failures for the efficacy analysis.

For the missing data of SMFA, in the case of the dysfunction index, unanswered items in a category are replaced by the individual's mean score for that category, as long as more than 50 percent of the items in that category have been answered. If $\leq 50\%$ of the items in that category have been answered, the missing data will not be imputed.

In the cases of missing or incomplete dates (e.g. AE and concomitant medications), the missing component(s) will be assumed as the most conservative value possible. For example, AEs with missing start dates, but with stop dates either overlapping into the treatment period or missing, will be counted as treatment-emergent, taking the worst-case approach. When partial dates are present in the data, both a partial start date and/or a partial stop date will be evaluated to determine whether it can be conclusively established that the AE started prior to the start of study drug or ended prior to the start of study drug. If the above cannot be conclusively established based on the partial and/or present dates, then the AE will be considered as treatment-emergent. Actual data values as they appear in the original case report forms (CRFs) will be presented in the data listings.

Missing values for other variables will not be imputed and only observed values will be used in data Analysis and summaries.

8.3. Baseline Definition

Baseline pathogen(s) are determined from all specimens collected prior to the first dose of study drug.

For all other efficacy and safety endpoints, the baseline value is defined as the last measurement or assessment prior to the first dose of study drug.

8.4. Subject Disposition

Subject disposition will be summarized for the ITT Population for each treatment group and in total. The following subject disposition categories will be included in the summary for all randomized subjects:

- Subjects who were randomized,
- Subjects who were treated,
- Subjects who were not treated,
- Subjects who completed the study, and
- Subjects who did not complete the study.

SAP MBN-101-201
Version 1.0, 19 July 2018

For subjects who did not complete the study, a summary will be provided by reason for discontinuation. The total number of subjects in each defined analysis population will be tabulated.

In addition, a summary of screen failures and the reason will also be tabulated for All Screened Subjects.

rgg **P** **P**

Demographic and baseline characteristics such as age, age group (<65 and \geq 65), gender, race, ethnicity, height, weight, BMI, and surgery site characteristics (type of injuries, method of fraction fixation, surgical site location), time from previous surgery to study enrollment, and type of previous treatment and current surgery characteristics (area of the osteosynthesis or osteomyelitis site, hardware removal, new hardware replacement, and method of wound closure) will be summarized with appropriate descriptive statistics (the number of observations, mean, standard deviation, median, minimum and maximum for continuous variables; number and percentage for categorical variables) by treatment group and overall.

Baseline characteristics summaries will be based on the Safety Population and repeated for the mITT and PK Concentration Populations.

rgg **P**

Distribution of Pathogens Isolated at Baseline will be tabulated by treatment group and overall for the mITT Population with any baseline pathogens.

rgg **P**

Medical History (Connective tissue disease/Autoimmune disease, HIV/AIDS, Renal disease, and Diabetes Mellitus) will also be summarized descriptively by treatment group and in total for the Safety and mITT Populations.

All medical histories will be listed by subject.

rgg **P** **P**

Prior medications are medications used before the first dose of study drug. Concomitant medications are medications that were taken on or after first dose of study drug.

The prior and concomitant medications will be summarized with the number and percentages by ATC class and preferred term for each treatment group and overall for the Safety and mITT Populations. Concomitant systemic antibiotic administered for treatment of the infected osteosynthesis/arthrodesis surgical site will also be summarized in the same manner. Although a subject may have taken two or more medications, the subject is counted only once within an ATC classification. The same subject may contribute to two or more preferred terms in the same classification.

All prior and concomitant medications and procedures will be listed by subject.

rgg **P**

All efficacy analysis will be based on the mITT Population.

8.9.1. Treatment Failure

The number and percent of subjects with treatment failure during the study will be tabulated by treatment group. If data permit, the difference in proportion of treatment failures between each treatment dose group and placebo group and the corresponding 95% exact confidence intervals for the difference will be presented. The Exact confidence interval will be calculated using the Clopper Pearson method.

Sensitivity Analysis for Treatment Failure

An 'as assigned' analysis will be performed on the mITT subjects as a sensitivity analysis for treatment failure. In this analysis, subjects who received a treatment that is not the assigned treatment will be included in the 'assigned' treatment group for this analysis.

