7. ANALYSIS POPULATIONS

The following analysis datasets will be identified for the purpose of analysis.

pgg **P**

All Screened Subjects will include all subjects who signed informed consent for the study.

pkg **f f** **R b**

Intent-to-Treat (ITT) Population will include all subjects who were randomized in the study. A randomized subject may or may not be treated with the assigned study drug.

pdg

Safety Population will include all subjects who received any amount of study drug (active or placebo). All treated subjects will be included in the safety analysis.

png **P f f a bP**

Modified Intent-to-Treat (mITT) Population will include the ITT subjects who received any amount of study (active or placebo) and have at least one post-treatment assessment. The mITT Population is the primary population for efficacy analysis. Post-treatment assessment includes any post-treatment assessment in any study data collected, for example, lab, vital sign, etc.

png **P**

PK Concentration Population will include all subjects with any measurable bismuth blood concentrations.

ppg **P**

PK Evaluable Population will include all subjects providing sufficient measurable bismuth blood concentrations to facilitate determination of PK parameters.

rg **P**

rgg **P P**

Summary statistics will be presented by treatment group. For continuous variables, the number of observations (n), mean, standard deviation (SD), median, minimum, and maximum will be provided. For categorical variables, the frequency and percentage in each category will be displayed.

For summary statistics, the mean and median will be displayed to one decimal place greater than the original value and the measure of variability (e.g. standard deviation) will be displayed to two decimal places greater than the original value. All Analysis will be performed using SAS® Version 9.3.

All safety and efficacy endpoints will be tabulated with descriptive statistics; data from all placebo subjects (2 per cohort; 6 subjects in total) will be pooled. Data from BisEDT treated subjects will be presented by dose (6 subjects per dose) and combined (a total of 18 subjects). If data permits, differences between the treatment groups and 95% confidence intervals for the difference will be presented.

In the event that a subject received study drug treatment that is not the assigned/randomized

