8.9.2. Incidence of Serious Interventions, Readmission, and Reoperation

The number and percent of subjects with at least one serious intervention, readmissions and reoperations (exclusive of serious interventions, readmissions, and reoperations associated with a healed bone site) and total number of serious interventions, readmissions and reoperations will be tabulated by treatment group for the following periods:

- duration of the study,
- within the first 4 weeks after the surgery,
- from week 4 to week 8; and
- from week 8 to week 12.

If data permit, the difference in proportion of the above incidences between each treatment dose group and placebo group and the corresponding 95% exact confidence intervals for the difference will be presented. The Exact confidence interval will be calculated using the Clopper Pearson method.

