8.9.4. Surgical Site Signs and Symptoms

The number and percentage of subjects with surgical site signs and symptoms including local erythema, induration, drainage and degree of healing will be summarized descriptively by treatment group at baseline and each scheduled post-baseline time point. The intensity of the signs and symptoms will be summarized as well. For each symptom, the difference in proportion of the above incidences between each treatment dose group and placebo group and the corresponding 95% exact confidence intervals for the difference will be presented. The Exact confidence interval will be calculated using the Clopper Pearson method.

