8.9.7. Microbiology

Microbiological success is assessed by clearance of infection, which is defined as eradication of all baseline pathogens.

The number and percentage of subjects with microbiological success will be tabulated descriptively by treatment group and time point. The difference in proportion of microbiological success between each treatment dose group and placebo group and the corresponding 95% exact confidence intervals for the difference will be presented. The Exact confidence interval will be calculated using the Clopper Pearson method.

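### SAP sections 8.9.1, 8.9.2, 8.9.4 and 8.9.7 name Clopper-Pearson, a one-proportion method, for the interval of a difference between two proportions, so those intervals cannot be calculated as written

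*SAP*

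**What the plan says.** SAP section 8.9.1 plans, where the data allow it, "the difference in proportion of treatment failures between each treatment dose group and placebo group and the corresponding 95% exact confidence intervals for the difference". The next sentence fixes the method: "The Exact confidence interval will be calculated using the Clopper Pearson method".

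The same pairing of a difference with Clopper-Pearson appears in three more places:

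- Section 8.9.2 (serious interventions, readmission, reoperation): "the difference in proportion of the above incidences between each treatment dose group and placebo group and the corresponding 95% exact confidence intervals for the" (quote cut short here), again only where the data allow it.
- Section 8.9.4 (surgical site signs and symptoms): "For each symptom, the difference in proportion of the above incidences between each treatment dose group and placebo group", with no such condition.
- Section 8.9.7 (microbiology): "The difference in proportion of microbiological success between each treatment dose group and placebo group", also with no condition.

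Section 8.1 (General Statistical Considerations) adds a broader promise that names no method: "If data permits, differences between the treatment groups and 95% confidence intervals for the difference will be presented". It also sets the group sizes: "data from all placebo subjects (2 per cohort; 6 subjects in total) will be pooled", and 6 active subjects per dose, 18 in all.

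No section plans a confidence interval for a proportion within one group, and no other method for a difference in proportions is named anywhere in the SAP.

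**The concern.** Clopper-Pearson inverts two one-sided binomial tests on one parameter. A difference between independent proportions involves two binomials and an unknown nuisance rate, so the named method does not produce the named quantity. The sentence cannot be rescued by reading it as referring to within-group rates, because these sections only tabulate counts and percentages within groups.

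At stake is what appears in the report for the clinical-activity objective. The analyst must either replace the method without authority from the SAP or improvise something from single-group limits and call it exact. With 6 subjects per group, different choices give visibly different limits, and the choice would be made after the data are available. In sections 8.9.4 and 8.9.7 the intervals are due in all cases, so the question cannot be avoided.

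**Working it through.** **Inputs from the SAP.** 6 subjects per dose, 18 active in total, 6 pooled placebo (section 8.1); 95% level (sections 8.9.1, 8.9.2, 8.9.4, 8.9.7). The SAP gives no expected event rates, so the event counts below are illustrative assumptions.

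**Step 1: the plan's own precision figures (section 4).** These concern one group.

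- Chance of at least one event in 6 at a rate of 0.385: 1 - (1 - 0.385)^6 = 0.946, against the stated 95%. The exact zero-event bound is 1 - 0.05^(1/6) = 0.393.
- Chance of at least one event in 18 at a rate of 0.153: 1 - (1 - 0.153)^18 = 0.950. The exact zero-event bound is 1 - 0.05^(1/18) = 0.153.

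Both agree closely with the plan. They are one-sample binomial statements, which is the setting where Clopper-Pearson applies. The plan states no figure for a between-group difference.

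**Step 2: what Clopper-Pearson gives.** For x events in n, the lower limit is the 0.025 quantile of Beta(x, n - x + 1) and the upper limit is the 0.975 quantile of Beta(x + 1, n - x). With n = 6:

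- 0/6: (0, 0.459)
- 1/6: (0.004, 0.641)
- 3/6: (0.118, 0.882)
- 4/6: (0.223, 0.957)

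For 1/6 versus 3/6 the output is two separate intervals and no interval for the difference of -0.333.

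**Step 3: two ways of improvising.**

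- Subtracting like limits for 1/6 versus 3/6: 0.004 - 0.118 = -0.114 and 0.641 - 0.882 = -0.241. The limits come out in reverse order and exclude the estimate of -0.333.
- Crossing the limits, (L1 - U2, U1 - L2): 0.004 - 0.882 = -0.878 and 0.641 - 0.118 = 0.523.

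The coverage of the crossed interval at 6 versus 6 was found by enumerating all 49 outcomes at each pair of true rates from 0.05 to 0.95 in steps of 0.05 (19 x 19 pairs). The minimum is 0.989 and the mean 0.999, against a nominal 0.95.

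**Step 4: an interval that does target the difference.** For each candidate difference D, compute T(D) = (x1/n1 - x2/n2 - D) / sqrt[p1(1 - p1)/n1 + p2(1 - p2)/n2], with p1 and p2 the maximum-likelihood rates under p1 - p2 = D. Keep D if both one-sided tail probabilities, each maximised over the nuisance rate, exceed 0.025. This is the exact unconditional score (Chan-Zhang) interval. Ordering outcomes by the raw difference instead gives the other exact interval shown.

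| Active v placebo | Crossed Clopper-Pearson | Exact, score | Exact, raw difference |
|---|---|---|---|
| 0/6 v 0/6 | -0.46 to 0.46 | -0.46 to 0.46 | -0.58 to 0.58 |
| 1/6 v 3/6 | -0.88 to 0.52 | -0.78 to 0.25 | -0.80 to 0.30 |
| 2/6 v 3/6 | -0.84 to 0.66 | -0.69 to 0.44 | -0.70 to 0.45 |
| 0/6 v 3/6 | -0.88 to 0.34 | -0.88 to 0.03 | -0.89 to 0.14 |
| 0/6 v 4/6 | -0.96 to 0.24 | -0.96 to -0.11 | -0.96 to -0.03 |

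For 1/6 versus 3/6 the widths are 0.52 + 0.88 = 1.40 (crossed) and 0.25 + 0.78 = 1.03 (score).

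**Step 5: when the choice moves zero in or out.** Over all 6 versus 6 tables, the crossed and score intervals disagree about zero only for 0/6 v 4/6, 0/6 v 5/6, 1/6 v 5/6, 1/6 v 6/6, 2/6 v 6/6 and their mirror images. All need a difference of at least four subjects out of six.

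**The case against.** The strongest reply is that little depends on these intervals. The primary objective is safety, safety is reported without inferential statistics, the sample size was chosen empirically with no hypothesis to test, and dose escalation rests on safety data. All of that stands, and it limits the importance of the point.

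Second, the plan nowhere tells anyone to cross single-group limits. Its request for an exact interval for the difference suggests that an exact unconditional interval was meant and the wrong name attached. That is fair: the coverage figures describe an assumed workaround, and one that errs towards over-coverage, so it would not manufacture an apparent benefit. But even on this reading the SAP has not said which exact interval, and for 0/6 versus 3/6 the upper limit is 0.03 or 0.14 depending on the ordering statistic.

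Third, a reader might infer that every planned between-group interval is wrong, or that these are the only between-group measures of uncertainty for clinical activity. Section 8.1 supports neither. It promises intervals for differences in general and names no method, so those intervals are unspecified and not wrong through Clopper-Pearson.

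Fourth, a reader might add that limiting these contrasts to each dose versus placebo is itself a fault, since section 8.1 also presents the 18 active subjects combined. It is not an error. Per-dose contrasts are a reasonable choice in a three-dose escalation study, and pooling concentrations from 0.025 to 0.25 mg/mL, a tenfold range, could hide a dose response.

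**Conclusion.** The point holds for the four named sections: the method stated there cannot give the interval stated there, and nothing else in the SAP supplies one. It should be fixed before the analysis, but it is not critical. It touches secondary, descriptive efficacy results only.

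The size depends on what the programmer does instead. Under crossing, coverage is at least 98.9% over the rates examined, and the interval for 1/6 versus 3/6 is 1.40 wide against 1.03. The difference is not uniform: at 0/6 versus 0/6 the crossed and score intervals coincide. It would be tempting to say that the choice of method generally decides whether an interval excludes zero. That is true only for extreme tables, and the plan attaches no test to zero.

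The assumptions are the planned 6 per dose and 6 pooled placebo, independent binomial counts, and illustrative event counts.

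**What to change.** In sections 8.9.1, 8.9.2, 8.9.4 and 8.9.7, replace the sentence naming Clopper-Pearson with:

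> The 95% CI for the difference will be the exact unconditional interval based on the score statistic (Chan-Zhang); Clopper-Pearson will be used only for any single-group proportions.

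Naming the score statistic matters, since exact unconditional alone still leaves the ordering open. The cost is an edit to four sentences and the matching programming specification. No new data, design change or extra subjects are needed.

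A combined active versus pooled placebo contrast (18 versus 6) is optional and not part of this correction. By the same score method its interval for 3/18 versus 3/6 is about -0.73 to 0.10, a width of 0.83 against 1.03 for 1/6 versus 3/6. If added, it should accompany the per-dose contrasts and not replace them.

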8.9.2. Incidence of Serious Interventions, Readmission, and Reoperation

The number and percent of subjects with at least one serious intervention, readmissions and reoperations (exclusive of serious interventions, readmissions, and reoperations associated with a healed bone site) and total number of serious interventions, readmissions and reoperations will be tabulated by treatment group for the following periods:

- duration of the study,
- within the first 4 weeks after the surgery,
- from week 4 to week 8; and
- from week 8 to week 12.

If data permit, the difference in proportion of the above incidences between each treatment dose group and placebo group and the corresponding 95% exact confidence intervals for the difference will be presented. The Exact confidence interval will be calculated using the Clopper Pearson method.

8.9.3. Time-to-Event Efficacy Endpoints

The following time-to-event efficacy endpoints will be summarized descriptively using the Kaplan-meier estimator by treatment group:

- Time to the first serious intervention exclusive of serious interventions, readmissions, and reoperations associated with a healed bone site
- Time to readmission (exclusive of readmissions associated with a healed bone site)
- Time to reoperations (exclusive of reoperations associated with a healed bone site)
- Time to removal of hardware due to a healed bone site

Time to first serious intervention will be calculated as the number of study days from the study surgery date to the event onset date plus 1. Subjects who do not have any serious intervention will be censored to the last observation date.

Time to readmission will be calculated as the number of study days from the initial hospital discharge date to the hospital readmission date plus 1. Subjects who do not have any readmission will be censored to the last observation date.

Time to reoperation will be calculated as the number of study days from the study surgery date to reoperation date plus 1. Subjects who do not have any reoperation will be censored to the last observation date.

Time to removal of hardware will be calculated as the number of study days from the study surgery date to the event date plus 1. Subjects who do not have any removal of hardware will be censored to the last observation date.

The number and percentage of subjects with the event and subjects censored will be tabulated by treatment group. Subjects who do not have the event will be considered censored. The Kaplan-Meier estimate of Q1, Q3, and the median time to the event and the associated 95% confidence interval will be presented for each treatment group. The Kaplan-Meier plot for each endpoint will be provided.

8.9.4. Surgical Site Signs and Symptoms

The number and percentage of subjects with surgical site signs and symptoms including local erythema, induration, drainage and degree of healing will be summarized descriptively by treatment group at baseline and each scheduled post-baseline time point. The intensity of the signs and symptoms will be summarized as well. For each symptom, the difference in proportion of the above incidences between each treatment dose group and placebo group and the corresponding 95% exact confidence intervals for the difference will be presented. The Exact confidence interval will be calculated using the Clopper Pearson method.

8.9.5. Patient-Report Outcomes

8.9.5.1. The Veterans RAND 12 Item Health Survey (VR-12) Questionnaire

VR-12 total score, physical health domain score (PCS), and mental health domain score (MCS) at each scheduled visit and change from baseline will be summarized descriptively by treatment group.

8.9.5.2. The Short Musculoskeletal Function Assessment Questionnaire (SMFA)

SMFA results include the scores of the dysfunction and the bother indices, which are calculated by summing up the responses to the items and then transforming the scores according to the formula: $(\text{actual raw score} - \text{lowest possible raw score}) / (\text{possible range of raw score}) \times 100$.

SMFA results and change from baseline will be summarized by visit and treatment group with descriptive statistics.

8.9.6. Pain Assessments

Surgical site pain score (VAS) and change from baseline will be summarized descriptively by treatment group at baseline and each scheduled post-baseline time point.

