Patients will be randomized 3:1 (active:control) to three successive doses (0.025, 0.075, or 0.25 mg/mL w:v) of MBN-101 (up to 8 mL, for a dose of up to 0.2, 0.6, or 2.0 mg, respectively) or placebo (diluent). Enrollment to the next dose cohort will not commence until an evaluation by the Data Review Committee (DRC) of all available safety data on all patients through Week 6 of study supports escalation to the next cohort.

PK assessments will be performed predose and at nominal 1, 6, 12, 24, 36, 48 (Day 2), 60, 72 (Day 3), 96 (Day 4), and 336 (Day 14; Week 2) hours after administration of study drug.

Patients will undergo study visits at Hour 48 and Weeks 2, 6 and 12. All patients will be followed for a total of 12 weeks after surgery.

I kg **P**

Twenty-four adult male or female patients meeting protocol-specified eligibility criteria may participate in the study, with the objective of having a total of 6 patients per dose level in the MBN-101-treated group and 6 patients in a pooled placebo-treated group.

I g g

Subjects will be randomized in a 3:1 (active:placebo) ratio up to 24 hours prior to surgery via a central randomization scheme.

I g g

This study is a single blind study; however, knowledge of treatment assignment should remain limited to those directly involved with the patient's surgical procedure and other individuals on a need to know basis. In order to provide unblinding data in an emergency in the absence of an individual privy to treatment assignment, sites will be provided with a numbered unblinding envelope corresponding to each numbered test kit the site is delivered. These envelopes will be securely stored in the pharmacy. The unblinding envelope specifies the treatment group of the kit and should only be opened when absolutely necessary. For treatment of adverse events, it should be assumed that the patient has received study drug, thus avoiding the need to unblind the patient. However, in the event the Investigator determines the randomization assignment information is required to treat the patient for an adverse event, the Medical Monitor should be contacted. If the Medical Monitor cannot be reached, the blind may be broken by opening the envelope. The site should document the unblinding process in the patient's source documents.

I g g **P**

[Table 1](#) presents the schedule of events of the study.

Table 1. Schedule of Events

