4. SAMPLE SIZE CONSIDERATIONS

Sample size (24) for this study was chosen empirically for the purpose of the study without any formal statistical hypothesis to be tested.

Six subjects will receive active drug in each dose cohort. With 6 subjects receiving active drug, the probability of observing at least one of 6 subjects in a dose cohort exhibiting an AE of a specific type is 95% if the true background incidence rate for that event-type were approximately 0.385 or greater. Hence, if an AE of a specific type is not observed in the study in a sample size of 6 subjects receiving active study drug at a given dose, one would “rule-out” this AE as having an incidence rate of more than 0.385 with 95% confidence.

Similarly, if a rare event of interest is not reported in the 18 subjects treated with the active study drug, one could conclude that the rate of the event would be 0.153 or less with 95% confidence.

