8.9.9. Serologic Markers

Serologic marker CRP and ESR values and the change from baseline for each scheduled visit will be summarized with descriptive statistics by treatment group.

The number and percentage of subjects with normal, abnormal clinically significant, and abnormal not clinically significant for each serologic marker will be tabulated by treatment group at each scheduled visit.

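### For pain, VR-12, SMFA, CRP and ESR, the SAP does not name the scale of the Section 8.1 group differences and specifies no baseline adjustment

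*SAP*

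**What the plan says.** The sections for the continuous activity endpoints are descriptive, and each covers both the value at a visit and the change from baseline.

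- Pain (8.9.6): "Surgical site pain score (VAS) and change from baseline will be summarized descriptively by treatment group at baseline and each scheduled post-baseline time point".
- SMFA (8.9.5.2): "SMFA results and change from baseline will be summarized by visit and treatment group with descriptive statistics". VR-12 (8.9.5.1) is handled in the same way.
- CRP and ESR (8.9.9): "Serologic marker CRP and ESR values and the change from baseline for each scheduled visit will be summarized with descriptive statistics by treatment group".

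None of these sections mentions a difference between groups. That comes from the general rule in Section 8.1: "If data permits, differences between the treatment groups and 95% confidence intervals for the difference will be presented". The rule names neither scale nor method. By contrast, the sections on treatment failure, serious interventions, signs and symptoms, and microbiology (8.9.1, 8.9.2, 8.9.4, 8.9.7) name the comparison, each dose against placebo, and an interval method.

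Section 8.3 defines baseline as the last value before dosing. Table 1 and Sections 5.1.5 and 5.1.6 schedule a pre-dose value for every one of these measures.

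**The concern.** Evaluating clinical activity is a secondary objective, and the dose-minus-placebo differences are what a reader would use to look for a dose trend. If they are unadjusted, a group that starts worse by chance tends to look better on change and worse on visit values. With groups this small, such gaps will be common. Because the SAP does not name the scale, the choice between two answers that can differ noticeably stays open until the data are seen. A covariate that would largely settle the matter is already being collected.

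**Working it through.** **Inputs from the SAP.** Active groups: "Six subjects will receive active drug in each dose cohort" (Section 4). Placebo: "data from all placebo subjects (2 per cohort; 6 subjects in total) will be pooled" (Section 8.1). So N = 24 in k = 4 groups of 6.

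**Assumptions.** The SAP gives no SD and no baseline-to-follow-up correlation (rho) for these measures. I take rho = 0.3, 0.5 and 0.7, equal SDs at both times, normality and complete data.

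**The plan's own figures.** The SAP has none on this point. The figures in Section 4 concern adverse events: 1 - (1 - 0.385)^6 = 0.946 and 1 - (1 - 0.153)^18 = 0.950. They agree with the stated 95% to rounding and have no bearing on these endpoints.

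**Step 1: size of a chance baseline gap, one dose v placebo.** SD of the difference in baseline means = sqrt(1/6 + 1/6) = 0.577 baseline SDs. The chance of a gap above 0.5 SD in either direction is 2 x [1 - Phi(0.5/0.577)] = 0.39.

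**Step 2: how much of the gap reaches each unadjusted difference.** Let D be the baseline gap. Given D, the follow-up difference is expected to be the effect plus rho x D. The change difference is the follow-up difference minus D, so it is expected to be the effect minus (1 - rho) x D. For D = 0.577:

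| rho | change: (1 - rho) x 0.577 | visit value: rho x 0.577 |
|---|---|---|
| 0.3 | 0.40 | 0.17 |
| 0.5 | 0.29 | 0.29 |
| 0.7 | 0.17 | 0.40 |

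The two shifts have opposite signs. In subjects with both values, the two differences therefore disagree by exactly D.

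**Step 3: interval width, ANCOVA against raw change in the same four-group model.** The variance of change is 2(1 - rho) and the ANCOVA residual variance is 1 - rho^2, so their ratio is (1 + rho)/2. The average penalty for covariate imbalance is 1 + 1/(N - k - 2) = 1 + 1/18 = 1.056. Residual degrees of freedom fall from 24 - 4 = 20 to 19, so the t quantile rises from 2.086 to 2.093, a factor of 1.003.

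Width ratio = sqrt[((1 + rho)/2) x 1.056] x 1.003

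| rho | formula | 20,000 simulated trials | narrower by |
|---|---|---|---|
| 0.3 | 0.831 | 0.830 | 17% |
| 0.5 | 0.893 | 0.891 | 11% |
| 0.7 | 0.950 | 0.948 | 5% |
| 0.9 | 1.005 | 1.003 | none |

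Break-even: 2/(1.056 x 1.003^2) - 1 = 0.88.

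**Step 4: against unadjusted visit values.** Section 8.1 leaves that scale open too. In the same simulations the width ratio was 0.98, 0.89 and 0.73 at rho = 0.3, 0.5 and 0.7.

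**The case against.** The strongest reply is that the endpoint sections ask only for descriptive summaries, that the Section 8.1 differences are conditional, and that the study tests nothing: "Sample size (24) for this study was chosen empirically for the purpose of the study without any formal statistical hypothesis to be tested". This settles the severity. It does not remove the point, because Section 8.1 still provides for differences with intervals and says less about them for these endpoints than the SAP says for the proportions.

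A second reply is that ANCOVA need not pay off in tiny samples. For a model fitted to one dose and placebo alone (N = 12), this has force: the width ratios are 0.87, 0.93 and 0.99 at rho = 0.3, 0.5 and 0.7, and above about 0.72 the adjusted interval is wider on average. That is a reason to fit all four groups together, where break-even moves to about 0.88.

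A third is that the calculation is idealised. Pain runs from 0 to 10, SMFA is transformed to a bounded scale, and missing values are mostly not imputed. This stands, so the percentages are indicative only.

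Three stronger readings are tempting, and the documents do not support them:

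- A reader might infer that these endpoints are compared only through raw change. Visit values are summarised as well, and Section 8.1 names no scale.
- A reader might infer that an unadjusted interval is invalid. In a randomised comparison, chance imbalance is part of the sampling variation that the interval already reflects. What is lost is efficiency.
- A reader might expect a larger gain. Setting a two-group t interval against a four-group ANCOVA gives 21%, 15% and 10%, but part of that comes from pooling the variance over four groups and not from baseline adjustment.

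**Conclusion.** The point holds as a minor one. For VR-12, SMFA, pain, CRP and ESR, the SAP allows group differences with 95% intervals but does not fix their scale and does not use the baseline value. A typical chance gap of 0.58 SD would move a change difference by 0.40, 0.29 or 0.17 SD at rho = 0.3, 0.5 or 0.7, and would move the visit-value difference the other way. Adjustment in one four-group model narrows the interval by about 17%, 11% and 5% against raw change, and does nothing useful above rho of about 0.88.

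These sizes rest on assumed correlations, equal SDs, normality and full data. Step 1 also treats the baseline gap as pure chance. Placebo is pooled over successive cohorts, so four of the six placebo subjects in any dose comparison come from other cohorts, and drift in case mix could add to the gap. No hypothesis test, sample-size figure or primary safety conclusion depends on this.

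**What to change.** Keep all descriptive tables in 8.9.5, 8.9.6 and 8.9.9. Add that the Section 8.1 differences for these endpoints will come from one exploratory ANCOVA per endpoint and visit. It would have treatment group (three doses and pooled placebo) as factor and the baseline value as covariate. CRP and ESR would be analysed on the log scale, which is a judgement about their likely skewness. Report each dose minus placebo, and combined active minus placebo, with 95% confidence intervals.

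The cost is a few sentences of SAP text and one model per endpoint and visit, with no new data. Statistically, it takes one residual degree of freedom (19 instead of 20 when all 24 subjects contribute), a small penalty for covariate imbalance, and the assumption of a common baseline slope across groups.
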